3.8 Pharmacokinetics

Pharmacokinetic analysis will be based on the PK analysis set. Drug concentration data for MEDI3506 and Dapagliflozin for all randomized subjects will be provided.

Descriptive statistics of MEDI3506 serum concentrations by treatment group and visit overall and also by ADA category (TE-ADA negative, TE-ADA positive, ADA negative) will be reported.

Descriptive statistics of plasma concentration of Dapagliflozin by visit will also be reported.

Figures of geometric mean serum concentration of MEDI3506 versus time by dose and Dapagliflozin versus time will be provided. In addition, spaghetti plots of individual serum MEDI3506 concentrations over time by dose and by ADA category (TE-ADA negative, TE-ADA positive, ADA negative) will also be provided.

The pharmacokinetic data may be merged with those from other clinical studies for a model-based population PK analysis. If performed, these analyses will be reported outside of the CSR. Exposure-response relationships for both efficacy, safety or biomarker endpoints may be performed. Results of these analysis will be not reported in the CSR.

CCI [REDACTED]

[REDACTED]

[REDACTED]

CCI [REDACTED]

[REDACTED]

[REDACTED]

[REDACTED]

APPENDIX

The image shows the letters 'CCI' in a large, bold, red, sans-serif font. The letters are set against a solid black rectangular background. The 'C's are slightly open at the top and bottom, and the 'I' is a simple vertical bar.

A 3 Safety Analysis

Safety analysis will be based on the Interim Safety Analysis set. Selected safety outputs will be presented by treatment group and overall. The interim safety analysis will be performed

on the same subjects as the Full Analysis Population (FAP), but evaluated according to the actual treatment they received. If there is no dosing error, this is exactly the same population as the FAP.

The safety and tolerability criteria are defined and tabulated below. When either the Go or Amber criteria are met, it will be considered as acceptable.

Table 4: Safety and Tolerability Go/No Go Criteria

	GO in line with current safety profile	Amber change in safety profile with potential impact on label or development	Alert major impact on label of continued development
Overall Tolerability	Tolerability not an important barrier to adherence with < 10 % discontinuation due to AEs related to MEDI3506	Tolerability may impact adherence with $\geq 10 - 25$ % discontinuation due to AEs related to MEDI3506	Tolerability has a meaningful impact on adherence with ≥ 25 % discontinuation due to AEs related to MEDI3506
Hypersensitivity	No imbalance in serious anaphylactic reactions with base case (i.e. perfunctory) contraindication statement only	Increased frequency of serious hypersensitivity reactions that results in labelling beyond base case contraindication	Occurrence of major anaphylactic-type reactions or high frequency of hypersensitivity reactions that negatively impact benefit/risk assessment
Serious infections	No clinically meaningful imbalance in infections of any type, particularly severe intensity or serious events	Clinically meaningful increased frequency of nonserious infections and/or relatively increased frequency (5 – 10 patients more than placebo)* serious infections	Dose-dependent meaningfully increased frequency of serious infections (>10 patients on highest dose relative to placebo)* and a relatively increased frequency (3 – 5 patients on highest dose relative to placebo)* of fatal infections impacting the benefit/risk ratio of MEDI3506
Progression of heart failure	No clinically meaningful imbalance in HF-related AEs	Clinically meaningful increased frequency of HF-related AEs (5 – 10 patients more than placebo)*	Dose-dependent meaningful increase of hospital admissions for HF (>10 patients on highest dose than placebo)* or a relatively increased frequency (3 – 5 patients more than placebo)* of deaths due to HF that impacts on benefit/risk evaluation of MEDI3506

* The cut-off target patient numbers presented in the criteria above should be used as an approximation and interpreted in context of the overall B/R profile of MEDI3506

The number, percentage and percentage per patient exposure year (PEY) of participants reporting TEAEs in each treatment group will be tabulated by system organ class and preferred term; by system organ class. A summary of adverse events in any category will be presented by treatment. The incidence of common ($\geq 5\%$ of participants in any treatment group) TEAEs, common treatment-emergent serious AEs (TESAE), and AEs leading to discontinuation of study medication will be summarized by system organ class, preferred term and treatment group, sorted in decreasing overall (across treatments) frequency. Moreover, TEAEs leading to hospitalization will also be presented.

Listings will be presented of participants with SAEs, AEs leading to discontinuation, and participants who died. A listing will be presented of participants with AEs, detailing whether these are SAEs, AEs leading to discontinuation, or result in death.

Summary statistics of laboratory data will be presented. Participants with laboratory values which are highlighted as abnormal will be listed. Summary statistics of vital signs data may be collected.

SIGNATURE PAGE

This is a representation of an electronic record that was signed electronically and this page is the manifestation of the electronic signature

Document Name: d9183c00001-sap-ed-6		
Document Title:	Statistical Analysis Plan Edition 6	
Document ID:	Doc ID-004810933	
Version Label:	6.0 CURRENT LATEST APPROVED	
Server Date (dd-MMM-yyyy HH:mm 'UTC'Z)	Signed by	Meaning of Signature
05-Jul-2023 20:20 UTC	PPD	Content Approval

Notes: (1) Document details as stored in ANGEL, an AstraZeneca document management system.

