3.6.7 Data and Safety Monitoring Board

An independent DSMB has been formed to evaluate safety data from concurrently conducted MEDI3506 Phase 2 clinical studies in other indications. The DSMB will have access to data aggregated by treatment group and will be able to review collected study data by treatment while the study is ongoing. The DSMB will review prespecified data periodically to ensure subject safety and make recommendations to the sponsor regarding further conduct of the study. A separate charter will detail the rules, meeting frequency and scope of the responsibilities of the DSMB.

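### Table 4's serious-infection Alert joins its two limits with *and*, so an excess of fatal infections can still be rated Amber and acceptable; the heart-failure row uses *or*

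*SAP*

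**What the plan says.** All of this stands in the SAP, Appendix A 3 (Safety Analysis), Table 4, unless stated otherwise.

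- **Serious infections, Alert:** "Dose-dependent meaningfully increased frequency of serious infections (>10 patients on highest dose relative to placebo)* and a relatively increased frequency", completed by "3 – 5 patients on highest dose relative to placebo)* of fatal infections impacting the benefit/risk ratio of MEDI3506". One connective, *and*, joins the serious-infection limit to the fatal-infection limit.
- **Serious infections, Amber:** a clinically meaningful rise in nonserious infections and/or a "relatively increased frequency (5 – 10 patients more than placebo)* serious infections". The cell has no condition on deaths and does not say which dose is compared with placebo.
- **Consequence (lead-in to the table):** "When either the Go or Amber criteria are met, it will be considered as acceptable".
- **Progression of heart failure, Alert:** "Dose-dependent meaningful increase of hospital admissions for HF (>10 patients on highest dose than placebo)* or a relatively increased frequency", followed by 3–5 excess deaths due to heart failure. Here the connective is *or*.
- **Footnote to the starred numbers:** they "should be used as an approximation and interpreted in context of the overall B/R profile of MEDI3506".
- **Other provisions:** "Listings will be presented of participants with SAEs, AEs leading to discontinuation, and participants who died" (Appendix A 3). "The DSMB will have access to data aggregated by treatment group" (section 3.6.7).

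The appendix text before A 3 is redacted. The visible text does not say which category prevails when Amber and Alert are both met.

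**The concern.** For infections, an excess of deaths on the highest dose does not by itself move the stated category out of acceptable. For heart failure it does, and nothing visible explains the difference. The infection row fails at both ends:

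- With 5–10 excess serious infections, any number of excess deaths leaves the result in Amber.
- Above 10 excess serious infections but below 3 excess deaths, the result passes Amber's count and misses the Alert. It is clearly not Go, so the counts give it no category, although Amber's uncounted nonserious limb might still apply.

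What is at stake is whether the recorded category means what a reader of the interim report would take it to mean.

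**Working it through.** **1. The logic of the row.** Let S be the excess of patients with serious infections and F the excess of fatal infections, highest dose minus placebo. Three readings are needed. The fatal limit of 3–5 is taken as F ≥ 3. Amber's excess is taken as highest dose against placebo. The Alert's dose-dependence condition is ignored.

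- As written: Alert if S > 10 and F ≥ 3; Amber if 5 ≤ S ≤ 10.
- With *or*: Alert if S > 10 or F ≥ 3.

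| S | F | As written | With *or* |
|---|---|---|---|
| 4 | 3 | not Alert, below Amber's count | Alert |
| 8 | 2 | Amber | Amber |
| 8 | 4 | Amber, acceptable | Alert |
| 10 | 5 | Amber, acceptable | Alert |
| 11 | 2 | no category by count | Alert |
| 11 | 3 | Alert | Alert |

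For S from 5 to 10 and F from 3 to S there are 3+4+5+6+7+8 = 33 combinations. All 33 are Amber as written and Alert with *or*. For S from 11 to 20 and F from 0 to 2 there are 10 × 3 = 30. All 30 meet neither the Alert nor Amber's 5–10 band as written, and all are Alert with *or*. One word therefore repairs both ends.

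**2. How often it could matter (illustration only).** The SAP randomizes 140 subjects each to 300 mg and placebo. The interim size is not visible, so 140 and 70 per arm are both assumed, and all event rates are assumptions. Fatal infections are a subset of serious ones. In an arm of n with serious rate ps and fatal rate pf, fatal cases are Bin(n, pf), and serious cases equal fatal cases plus Bin(n − fatal, (ps − pf)/(1 − pf)). The distribution of (S, F) is the exact convolution of the two arms.

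Serious-infection rates, placebo v drug: 5% v 10%, 2% v 7%, 8% v 13%. Fatal rates on placebo: 0.5%, 0.2%, 1%. Fatal rates on drug, in the same order: 1%, 0.7%, 1.625% (case fatality equal in both arms); 2%, 1.4%, 3.25% (doubled); 3.5%, 3%, 4% (raised 3.5-, 4.3- and 2.5-fold).

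| 140 per arm | Alert, *and* | Alert, *or* | S 5–10 with F ≥ 3 |
|---|---|---|---|
| Equal case fatality | 2–8% | 19–35% | 4–8% |
| Doubled on drug | 8–20% | 34–64% | 16–27% |
| Raised 2.5- to 4.3-fold | 15–22% | 75–78% | 34–49% |

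With equal case fatality, 13–17 points of the rise are results with S > 10 and F < 3, that is, the second gap and not the excess of deaths. At 70 per arm, results with S 5–10 and F ≥ 3 occur in 1–4% (equal) or 19–21% (raised).

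Because dose dependence is ignored, probabilities that involve the > 10 limb are upper limits.

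**3. The price of *or*.** With no true difference, the chance of an Alert under *or* is:

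| Serious, fatal rate in both arms | 140 per arm | 70 per arm |
|---|---|---|
| 2%, 0.2% | 0.2% | 0.03% |
| 5%, 0.5% | 2.1% | 0.4% |
| 8%, 1% | 7.0% | 1.9% |

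**The case against.** - **The table guides judgement and is not an algorithm.** The footnote says so, the cells mix counts with clinical meaningfulness, and no visible text makes any action follow automatically from a category. This stands and limits the weight of the point. It does not remove it: the footnote softens the numbers but leaves the connective and the acceptability sentence as they are.
- **The *and* may be deliberate.** Fatal infections are a subset of serious ones, whereas a heart-failure death can occur without an admission, so the two rows are not exact parallels. The SAP gives no reason either way. A deliberate *and* would still leave results above 10 serious infections with few deaths unclassified by count. If *and* was meant to list two separate triggers, *or* says that more clearly.
- **Amber may refer to another dose.** Its cell does not name one, so the worked example depends on reading it as the highest dose.
- **Redaction.** A precedence rule may stand in the hidden text. It would not help in the example, because with 8 excess serious infections the Alert is not met at all.
- **Timing.** Interim details entered the SAP in version 3.0, and version 6.0 is an update for the final analysis, so the interim may be past.

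A reader might infer that an excess of fatal infections could pass the interim unnoticed. The documents do not support that: deaths and SAEs are listed, TEAEs are tabulated by treatment group, and the DSMB reviews data by treatment. A reader might also take the larger percentages as the expected frequency of the problem. They rest on assumed fatal-infection rates of 3–4% on drug, 4 to 15 times the assumed placebo rates.

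**Conclusion.** The infection Alert is misworded. As it stands, 5–10 excess serious infections with 3 or more excess deaths falls in a band called acceptable, and more than 10 with fewer than 3 excess deaths meets neither the Alert nor Amber's count. The logical fault rests on the visible wording, on reading 3–5 as at least 3, and on taking Amber's excess as highest dose against placebo. Its frequency cannot be established from the SAP, because interim size, infection rates and case fatality are all assumed. Given the footnote, the listings, the DSMB and the redacted interim text, this is a fault in a guide criterion and not the loss of a safeguard. Severity: minor.

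**What to change.** In the serious-infection Alert cell replace *and* with *or*. Write the death limit as ≥ 3 in both the infection and the heart-failure rows, so that 6 or more deaths is plainly covered. State that Alert prevails when Amber is also met.

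Keeping *and* and only capping deaths in the Amber cell is not enough: 5–10 excess serious infections with 3 or more excess deaths would then fall in no category.

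The change takes one word, two limits and one sentence, with no extra data. The price is the chance Alerts shown above, about 0.2–7% at 140 per arm and 0–2% at 70 per arm.

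If the interim has been run, leave the table unchanged and report the excess serious and excess fatal infection counts beside the category assigned. That costs two numbers, which come from data already listed and tabulated.
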